We will utilize connectome-based neurofeedback to assess patterns of functional connectivity within a previously identified “opioid abstinence network”. This network was identified using a whole-brain machine learning approach and predicted subsequent opioid relapse among methadone-maintained individuals. This network was robust, relatively unchanged in follow-up analyses controlling for other clinical variables (e.g., methadone dose, years of opioid use), predicted opioid relapse from different fMRI tasks as well as resting state, and predicted opioid use at multiple time points (two scanning sessions conducted 3 months apart). Design: Individuals on methadone (N=24) will receive active (n=24) connectome-based neurofeedback at 3 weekly scanning sessions (training scans 1-3). Training scans will include both feedback and transfer (i.e. no feedback) runs. Baseline (one week prior to training scan 1) and follow-up (one week following training scan 3) scans will be conducted to test the effects of feedback training on intrinsic connectivity during resting state and fMRI tasks, as in our pilot data. Clinical features of OUD (opioid use, craving, negative affect) will be assessed weekly and at one month follow-up.

Aim 1. To determine if connectome-based neurofeedback is associated with reduced opioid use. Aim 1a. We predict that individuals who receive active feedback will report lower

IRB# 2000025618

levels of opioid use from baseline to follow-up scans. *Aim 1b*. We predict that this reduction will persist over time as assessed at 1-month follow-up.

Aim 2. To determine if connectome-based neurofeedback is associated with changes in intrinsic connectivity. *Aim 2a*. Based on evidence that neurofeedback induces changes in intrinsic connectivity[13], we predict that subjects receiving active feedback will show increased opioid abstinence network connectivity during resting state at follow-up versus baseline scans. *Aim 2b*. We predict that this effect will generalize to increased connectivity during fMRI reward and cognitive tasks at these timepoints.

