Aim 3. To determine if connectome-based neurofeedback is associated with greater improvements in clinical features of opioid use disorder than sham feedback. *Aim 3a*. We predict that subjects who receive active feedback will show reduced craving and negative affect at follow-up versus baseline scans. *Aim 3b*. We predict that increased opioid abstinence network connectivity during transfer (no feedback) runs will be correlated with reduced craving and negative affect.

This proposal is significant by testing for the first time the effects of neurofeedback on large-scale network dynamics among individuals with opioid use disorder. This is a critical step toward understanding the neurobiology of opioid relapse and will pave the way for further treatment-oriented research.

2. **Probable Duration of Project:** State the expected duration of the project, including all follow-up and data analysis activities.

5 years

3. **Background:** Describe the background information that led to the plan for this project. Provide references to support the expectation of obtaining useful scientific data.

Write here

Need to understand brain functions in methadone treated individuals: Opioid use disorder (OUD) is a significant public health problem with opioid-associated overdoses and deaths rising significantly in recent years[14-16]. Methadone is a widely used and generally effective treatment for OUD, yet relapse rates remain high and treatment retention durations are suboptimal (e.g., <6 months in 30-50% of settings)[17-19]. As risk of overdose is highest following unsuccessful treatment (i.e., during a relapse)[20], improved mechanistic understanding of factors contributing to relapse in methadone patients is urgently needed to inform development of adjunct interventions to improve outcomes. We will leverage recent advances in connectome-based neurofeedback to probe large-scale patterns of brain functional connectivity previously linked to relapse among methadone-treated individuals with OUD. This is critical to improve our understanding of mechanisms contributing to relapse and an essential first step toward development of improved, evidence-based relapse prevention strategies.

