Rt-fMRI in addiction: Rt-fMRI is a powerful method for individualized assessment of patterns of brain functions and of individual abilities to regulate such functions, yet most studies fail to demonstrate clinical benefits[36]. Most rt-fMRI studies in addiction have focused on drug cue-reactivity and craving, typically providing feedback as mean activation in a brain region of interest (ROI). Most of this work has focused on smoking. Studies have shown that smokers are able to reduce cue-reactivity in targeted brain regions and reduce subjective craving[37, 38], yet only one study has used a control group[37] and none have measured effects on smoking. More recent work suggests that including functional connectivity in the feedback signal leads to greater reduction of nicotine craving compared with ROI feedback alone[6]. Preliminary evidence exist that individuals with alcohol use disorder can learn to modulate brain activity during alcohol cue exposure[39, 40] including transfer to a no feedback run[40]. Yet, no prior study has applied rt-fMRI feedback to assess neural network function among individuals with OUD. More advanced rt-fMRI methods may lead to more clinically meaningful outcomes. In particular, providing feedback from functional connectivity rather than ROI activation may be more clinically relevant[41]. Machine learning and meta-analytic data indicate that many behaviors including substance use rely on the orchestrated activity of a distributed array of brain regions[7-12]. Therefore, the best feedback signal is not likely to be the magnitude of activity in a single brain region, but the degree to which activity is coordinated across large-scale brain networks. Accordingly, feedback from functional connectivity has become the focus of studies examining connections (edges) between pairs of nodes or networks[42-44] and recent data indicate utility of this approach in addictions[6]. Moreover, most predictive brain models of behavior utilize connectivity derived from hundreds of regions and thousands of edges, rather than a single edge[10, 11, 30, 31, 45]. To realize its promise, rt-fMRI in addiction must provide feedback based

on complex large-scale brain networks—e.g., empirically defined networks derived from whole-brain machine learning methods such as the opioid abstinence network.

Table 1: Study overview	Baseline	Training 1-3	Follow-up	1 mo.
Resting state fMRI	X	X	X	
Rt-fMRI Training runs		X		
Rt-fMRI Transfer runs	X	X	X	

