Baseline and follow-up scans: Will include resting state (10 min), cognitive task (Stroop[51, 52]; 10 min), reward task (monetary incentive delay[48, 53, 54]; 10 min), and a transfer task (5 min; see below); collected using a T2* sensitive gradient-recalled single shot echo planar pulse sequence. A high-resolution T1-weighted 3D anatomical scan will be acquired at the baseline scan using a magnetization prepared rapid gradient echo sequence.

Training scans: Subjects will perform five 5-minute runs of active neurofeedback and a 5-minute transfer run before and after the feedback runs. Table 1 summarizes data collection. fMRI data will not be multiband due to the need to reconstruct and process data in real-time.

Other measures: Participants will be given self-report measures of general intellectual function (Shipley Institute of Living Scale[55]), impulsivity (UPPS impulsive behavior scale[56]), negative affect (Quick Inventory of Depressive Symptomatology[57]), craving (Opioid Craving Scale[58]) and withdrawal (Clinical Opiate Withdrawal Scale[59]). As previously noted, these measures may be collected in-person but in an effort to reduce the amount of time participants are physically present at the MRRC we will perform this data collection remotely whenever possible.

Imaging parameters: MRI data will be collected with a 3T Siemens Primsa system and 32-channel head coil. Functional runs will be acquired using an EPI sequence with the following parameters: TR = 2000 ms, TE = 25 ms, flip angle = 90°, acquisition matrix = 64 × 64, in-plane resolution = 3.5 mm², 34 axial-oblique slices parallel to the AC-PC line, slice thickness = 4. Parameters of the anatomical MPRAGE sequence were as follows: TR = 1900 ms, TE = 2.52, flip angle = 9°, acquisition matrix = 256 × 256, in-plane resolution = 1.0 mm², slice thickness = 1.0 mm, 176 sagittal slices. A 2D T1-weighted image coplanar to the functional images was collected for registration.

Connectome-based neurofeedback uses a similar approach to CPM (described above) but summarizes connectivity for a previously defined predictive network, here calculated in real time and used to construct a feedback signal (**Fig 1**).

[figure not shown]

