Aim 2: *To determine if connectome-based neurofeedback is associated with changes in intrinsic connectivity.* H2a. Subjects receiving active versus sham feedback will show increased opioid abstinence network connectivity between resting state acquired at follow-up versus baseline scans. H2b. This effect will generalize to increased connectivity during fMRI reward and cognitive tasks as in our pilot data.

Approach: Opioid abstinence network connectivity strength will be calculated during resting state (H2a), MIDT and Stroop tasks (H2b) as in our pilot data, and will be entered into a linear mixed effects model with the between-subject factor of feedback group (active/sham) and the within-subject factor of time (baseline/follow-up scans).

Aim 3: *To determine if connectome-based neurofeedback is associated with greater improvements in clinical features of OUD than sham feedback.* H3a. Subjects receiving active versus sham feedback will show reduced craving and negative affect at follow-up versus baseline scans. H3b. Increased opioid abstinence network connectivity during transfer runs will be correlated with reduced craving and negative affect.

Approach: Craving (Opioid Craving Scale) and negative affect (Quick Inventory of Depressive Symptomatology) will be calculated at follow-up and baseline scans and compared between groups using repeated measures analysis of variance. Change in opioid abstinence network connectivity strength will be calculated during transfer runs at baseline and follow-up scans. We will test for Pearson's correlations between change in connectivity strength and changes in craving and negative affect.

5. **Genetic Testing** N/A

6. **Subject Population:** Provide a detailed description of the types of human subjects who will be recruited into this study.

IRB# 2000025618

Write here

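### If all 24 participants get active feedback, the baseline-to-follow-up change in Aims 2a and 3a mixes feedback with other change, and the scheduled feedback-free week before training scan 1 is not used to show it

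*Combined protocol and SAP*

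**What the plan says.** The Statement of Purpose (Section I.1) sets out a single arm: "Individuals on methadone (N=24) will receive active (n=24) connectome-based neurofeedback at 3 weekly scanning sessions (training scans 1-3". The study design paragraph of the Research Plan (Section I.4) also gives 24 active. On timing, "Baseline (one week prior to training scan 1) and follow-up (one week following training scan 3) scans will be conducted". No feedback is given between baseline and training scan 1.

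The Section I.1 predictions are before-after statements. Aim 2a is that "subjects receiving active feedback will show increased opioid abstinence network connectivity during resting state at follow-up versus baseline scans"; Aim 3a is that "subjects who receive active feedback will show reduced craving and negative affect at follow-up versus baseline scans".

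Table 1 marks the rows "Resting state fMRI" and "Rt-fMRI Transfer runs", and the craving and affect row, at baseline, training 1-3 and follow-up. Task fMRI is marked at baseline and follow-up only. The training-scan paragraph of Section I.4 says: "Subjects will perform five 5-minute runs of active neurofeedback and a 5-minute transfer run before and after the feedback runs". It lists no resting-state run.

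Under Hypothesis testing (Section I.4), the Aim 2 model has an active/sham factor and "the within-subject factor of time (baseline/follow-up scans". Aim 3a compares groups on baseline and follow-up values. Section I.13 repeats both factors for Aims 2 and 3 and justifies the sample as 12 per group. Hypothesis testing opens by saying that connectivity from every scanning session will be entered, but no stated model uses the training-session values.

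**The concern.** Under a single arm, nobody shows what network strength, craving and affect do without training. Familiarity with the scanner, practice and the passage of four weeks can all move them.

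The protocol itself adds two selection effects. Excessive motion at the baseline scan is an exclusion, and Section I.4 acknowledges that connectivity is very sensitive to motion, so baseline is selected for stillness and follow-up is not. Entry also requires evidence of recent opioid use, so craving and affect may settle back on their own.

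Any of these would appear in the time effect that is meant to answer Aims 2a and 3a. The schedule holds one interval that bears on the question, and no stated analysis uses it.

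**Working it through.** **The plan's own figure.** Section I.13 gives noncentrality 5.36, critical t 2.10, df 18 and power 0.99. A noncentral t at two-sided 0.05 gives critical t 2.10 and power 0.999, so the figure reproduces. It is for two groups of 10 with an implied d of 5.36/√(10/2) = 2.40. It says nothing about a single-arm change.

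**Inputs.** From the documents: n = 24, and four weekly intervals from baseline (B) to follow-up (F), with training scan 1 (T1) at the end of the first. Assumed, because the documents give none: equal correlation ρ between sessions of 0.3 to 0.7, and total drift D in units of the session SD.

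**Precision.** A contrast with coefficients c has variance Σc²·σ²(1−ρ)/n. At ρ = 0.5, F−B has SE √(2 × 0.5/24) = 0.204 SD. T1−B and F−T1 have the same SE, because Σc² = 2 for each. The 95% half-width is 2.07 × 0.204 = 0.42 SD, and the effect detectable with 80% power is 0.60 SD.

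**Effect of drift on F−B with zero feedback effect** (paired t, df 23, two-sided 0.05):

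| D | ρ = 0.3 | ρ = 0.5 | ρ = 0.7 |
|---|---|---|---|
| 0 | 0.050 | 0.050 | 0.050 |
| 0.1 | 0.068 | 0.076 | 0.093 |
| 0.2 | 0.125 | 0.156 | 0.228 |
| 0.3 | 0.222 | 0.291 | 0.444 |
| 0.5 | 0.509 | 0.650 | 0.857 |

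**What the lead-in can do.** Let drift be either linear, d per week (B = 0, T1 = d, F = 4d), or a one-off shift s at the first repeat (B = 0, T1 = F = s):

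| Contrast | Linear bias | One-off bias | Σc² | SE relative to F−B |
|---|---|---|---|---|
| F−B | 4d | s | 2 | 1 |
| F−T1 | 3d | 0 | 2 | 1 |
| F−(B+T1)/2 | 3.5d | s/2 | 1.5 | √0.75 = 0.87 |
| (F−T1)−(T1−B) | 2d | −s | 6 | √3 = 1.73 |
| (F−T1)−3(T1−B) | 0 | −3s | 26 | √13 = 3.6 |

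F−T1 removes a one-off shift at no loss of precision, but keeps three quarters of a linear drift. Only the last contrast removes linear drift. At ρ = 0.5 its SE is 0.736 SD and its detectable effect 2.15 SD, too imprecise to be useful.

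**The case against.** The strongest reply is that the Aim 2 sentence also contains the active/sham factor. With a concurrent sham group, drift shared by both groups cancels in group by time. This stands as a condition. A reader might infer that the plan counts drift as feedback whatever the design; the documents do not support that, because sham wording also survives in Aim 3 of Section I.1, Hypothesis testing in Section I.4, Section I.13 and the payments text in Section VI. The point holds only if the single-arm design text governs.

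A reader might also infer that the lead-in can stand in for a control group. It cannot, since it is one interval of four. Two tempting uses of it fail:

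- Testing follow-up against the mean of baseline and T1 gains precision, not protection. Under linear drift it keeps 3.5/4 = 87.5% of the bias with an SE 0.866 times as large, so bias over SE rises by 1% (0.875/0.866). At ρ = 0.5 and D = 0.3, false rejection goes from 0.291 to 0.296. For a one-off shift it falls only to 0.129.
- Crediting feedback when the main change exceeds the lead-in change would credit pure linear drift, because 4d (or 3.5d against the two-session mean) exceeds d.

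It is also fair that T1 does not match baseline: it has no Stroop or monetary incentive delay task and is not motion-screened. Only the transfer run is explicitly placed before feedback, and it serves H3b rather than Aims 2a or 3a.

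**Conclusion.** The concern holds conditionally. If all 24 are active, the group term cannot be estimated and the baseline-to-follow-up effect in Aims 2a and 3a cannot be assigned to feedback. The 13% to 44% false-rejection range rests wholly on assumed drift of 0.2 to 0.3 SD and correlations of 0.3 to 0.7; whether drift of that size occurs is unknown.

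Using the lead-in is an inexpensive improvement in what the trial can report, not a cure. It can show a first-repeat shift and, through F−T1, remove one. The equal SE of F−T1 and F−B depends on equal correlations and variances across sessions. H2b has the same confounding and no lead-in repeat. Reconciling the sham text comes first, because it decides whether this point applies.

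**What to change.** 1. Reconcile the 24-active design text with the sham wording in Section I.1 (Aim 3), Section I.4 (Hypothesis testing), Section I.13 (models and 12 per group) and Section VI (payments).
2. If single arm, reconcile Table 1 with the training-scan paragraph on whether resting state is acquired at training scans. State that the training-scan-1 resting-state run and the craving and affect questionnaires come before the first feedback run.
3. Keep follow-up versus baseline as the main contrast for Aims 2a and 3a.
4. Add to Sections I.4 and I.13: (a) the baseline-to-training-1 change with its 95% confidence interval, labelled as the change without feedback; and (b) follow-up minus training-1 pre-feedback as a supporting contrast. Do the same with the pre-feedback transfer run as support for H3b.
5. Describe any change as associated with the training period, not caused by feedback. Use neither the two-session mean nor an exceeds-the-lead-in rule as a correction for drift.

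Cost: run order at one session and a few sentences in two sections. No participant or visit is added, and no scan if Table 1 is right that resting state is already acquired at training scans. The supporting contrast is not fully like for like, and the report should say so.

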
4. **Research Plan:** Summarize the study design and research procedures using non-technical language that can be readily understood by someone outside the discipline. **Be sure to distinguish between standard of care vs. research procedures when applicable, and include any flowcharts of visits specifying their individual times and lengths.** Describe the setting in which the research will take place.

Study design: Participants will receive active ($n=24$) connectome-based feedback at three separate scanning sessions (training scans 1-3). . Training scans will include both neurofeedback and transfer (i.e., no feedback) runs conducted at weekly intervals (**Table 1**).

IRB# 2000025618

Additionally, to test the effects of feedback training on intrinsic

U-Tox	X	X	X	X
TLFB for substance use	X	X	X	X

connectivity, baseline (one week prior to training scan 1) and follow-up (one week following training scan 3) scans will be conducted and will include resting state and reward and cognitive task fMRI runs, to compare networks across brain states as in our prior work[49].

Screening visit: To determine eligibility subjects will first take part in a screening visit involving surveys about their health, smoking, substance use behaviors and attitudes, and the ways in which they view themselves. They will also complete a urine drug test. The screening session will take about 1 and ½ hours. If they are eligible, we will also schedule their MRI appointments during this visit.

Debriefing: At the end of the one month study visit, participants will be fully debriefed by study personnel, who will explain more thoroughly the purpose of the study and answer any questions they may have.

Opioid use: Opioid and other substance use will be monitored weekly at each MRI session from baseline to follow-up using urinalysis and the Timeline Followback (TLFB) [50] method, as in our prior work[10, 48]. Behavioral measures of clinical variables (e.g., pain, other substance use, craving and negative affect) will also be collected.

Imaging Protocol: Scanning will be conducted 2-3 hours following daily methadone on a 3T Siemens Prisma scanner with a 32-channel head coil. A member of the research staff will accompany each subject to the MRRC and stay with them for the duration of the study.

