We plan to enroll twenty-four individuals (12 male, 12 female) receiving methadone for OUD. Eligibility criteria: (i) non-methadone opioid positive urine screen (as assessed during standard treatment at APT) or indicated via Utox or self-reported past-month opioid use at screening); (ii) DSM-5 criteria for OUD, as assessed via structured clinical interview (SCID)[66]; (iii) ≥ 3 months of methadone treatment; (iv) eligibility for MRI; (v) age 18-50; (vi) baseline scanning with acceptable motion (i.e., <.15mm frame-to-frame displacement), as in prior work. Retention: APT patients attend clinic on a daily basis to receive methadone and this has contributed to high retention rates (e.g., 86% over three months) in our studies[10, 67] in this population.

7. **Subject classification:** Check off all classifications of subjects that will be specifically recruited for enrollment in the research project. Will subjects who may require additional safeguards or other considerations be enrolled in the study? If so, identify the population of subjects requiring special safeguards and provide a justification for their involvement.

 Children	 Healthy	 Fetal material, placenta, or dead fetus
 Non-English Speaking persons	 Prisoners	 Economically disadvantaged
 Decisionally Impaired fetuses	 Employees	 Pregnant women and/or
 Yale Students	 Females of childbearing potential	

NOTE: Is this research proposal designed to enroll children who are wards of the state as potential subjects?

Yes No

8. **Inclusion/Exclusion Criteria:** What are the criteria used to determine subject inclusion or exclusion?

Write here

- i. Inclusion criteria
 1. non-methadone opioid positive urine screen (as assessed during standard treatment at APT) or indicated via Utox or self-reported past-month opioid use at screening
 2. DSM-5 criteria for opioid use disorder, as assessed via structured clinical interview (SCID)
 3. ≥ 3 months of methadone treatment
 4. Age 18 to 50
- ii. Exclusion criteria
 1. Meet DSM-5 psychiatric classifications for lifetime schizophrenia or bipolar disorder with psychotic features, or exhibit significant current suicidal or homicidal plans and intent such that hospitalization is required

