 YCCI Recruitment database	 Social Media (Twitter/Facebook):	
 Other:		

IRB# 2000025618

We plan to collect full data from twenty-four individuals (12 M, 12 F) receiving methadone for OUD. Thus, in order to account for possible participant attrition, we will likely scan up to 40 individuals (and anticipate screening up to 100). Participants will be recruited via clinician referrals from the APT Foundation, one of the largest methadone providers in CT, consistent with our prior[48, 49] and ongoing work. While rates of other forms of medication-assisted treatment (e.g., buprenorphine, naltrexone) have increased in recent years, methadone remains the most prevalent treatment for OUD in the US[20], therefore, to reduce sample variability, this study will only recruit individuals treated with methadone. For regular attendance for methadone, APT patients meet regularly with clinicians, as per federal guidelines. [name] (Co-I), Director of Research for APT, is ideally suited to facilitate participant referral and longitudinal clinical assessment for this study.

* Requests for medical records should be made through JDAT as described at
<http://medicine.yale.edu/ycci/oncore/availableservices/datarrequests/datarrequests.aspx>

3. Recruitment Procedures:

- a. Describe how potential subjects will be identified. *Write here*
- b. Describe how potential subjects are contacted. *Write here*
- c. Who is recruiting potential subjects? *Write here*

Consistent with previous studies conducted by the PI and co-investigators, participants in methadone treatment for an opioid-use disorder will be recruited from the APT Foundation. Interested participants entering the methadone treatment program at APT will be referred by APT personnel to research staff when possible for eligibility screening. [name], a co-investigator for this study, is both the Director of Research and the Director of Pain Services for the APT Foundation, he is ideally suited to facilitate participant referral and longitudinal clinical assessment for this study. Participants may also be referred to the study by word of mouth from other participants. HIC approved recruitment materials will provide information about how to contact research staff to learn more about the study. All recruitment will be conducted by local HIC-approved study personnel who completed HIC training requirements.

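### Participants are selected on recent opioid use and all receive active feedback, so part of any fall from baseline in Aim 1 could occur without a feedback effect, and no planned analysis separates it out

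*Combined protocol and SAP*

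**What the plan says.** **Selection.** Section I, 6 (Subject Population) and Section I, 8 (Inclusion/Exclusion Criteria) admit a patient with a "non-methadone opioid positive urine screen (as assessed during standard treatment at APT"), "or indicated via Utox or self-reported past-month opioid use at screening". Any one of the three routes is enough. Both sections also require at least 3 months on methadone.

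**Design.** Section I, 1 (Statement of Purpose) states: "Individuals on methadone (N=24) will receive active (n=24) connectome-based neurofeedback at 3 weekly scanning sessions". Section I, 4 (Research Plan) repeats it: "Participants will receive active ($n=24$) connectome-based feedback at three separate scanning sessions".

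**Aim.** Aim 1 in Section I, 1 is "To determine if connectome-based neurofeedback is associated with reduced opioid use". Aim 1a predicts lower "levels of opioid use from baseline to follow-up scans", and Aim 1b predicts that the reduction lasts to 1 month.

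**Schedule.** "Baseline (one week prior to training scan 1) and follow-up (one week following training scan 3) scans will be conducted". Table 1 places feedback runs at the training scans only. Urine, TLFB, craving and affect are collected at baseline and at each training visit, so a week without feedback has measurements at both ends.

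**Analysis.** Hypothesis testing (Section I, 4) measures H1a as the percentage of negative urines over the five weeks from baseline to follow-up. There and in Section I, 13 (Statistical Considerations), Aim 1 is a linear model with an active/sham group factor. Section I, 13 still gives 12 per group, and the payment text in Section VI, 2 still says that some participants received sham. No section mentions regression to the mean, a lead-in comparison or pre-enrolment levels.

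**The concern.** Selecting people on recent use and then reading a later fall, with no concurrent control, is the standard setting for regression to the mean. If use comes in runs, patients are more likely to be enrolled during a run, and the group can drift down without any intervention. A baseline TLFB that reaches into the qualifying month makes this worse, because the selected period itself becomes the baseline.

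With 24 of 24 participants on active feedback, the active/sham factor has one level and cannot be estimated. The natural repair is to analyse within-person change from baseline, which is exactly the analysis exposed to this bias. What is at stake is the reading of Aim 1: a fall could be credited to neurofeedback when part or all of it came from how patients were chosen.

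**Working it through.** **1. The plan's own figure.** Section I, 13 gives noncentrality 5.36, df 18, critical t 2.10 and power 0.99 for N=10 per group. The 0.975 quantile of t at 18 df is 2.101, and power at noncentrality 5.36 is 0.999, so the figure reproduces. The implied standardised difference is 5.36/√(10/2) = 2.40. It concerns group differences in connectivity. No effect size or power is given for opioid use, so it does not bear on Aim 1.

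**2. What H1a mixes.** There are five scanning visits: baseline, three training scans and follow-up. The baseline and training-scan-1 urines reflect use before any feedback, so 2 of 5 (40%) are pre-feedback. If every later urine changed by D points, the pooled percentage would move by (3/5)D = 0.6D. It has no change-from-baseline term.

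**3. Fall with no feedback effect (simulation).** The documents give no use rates, so these inputs are assumptions:
- daily use on the logit scale, mean −4 to −1, with a stable person level (SD 1.5);
- weekly fluctuation, SD 1 to 2, autocorrelation 0 to 0.85;
- urine detects about 3 days of use;
- entry by the either/or rule, baseline one week after screening, follow-up four weeks after baseline;
- paired t-test, n=24, two-sided 5%, so 2.5% in the direction of a fall.

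Results:
- *Urine, either/or entry:* fall of 0 to about 4 points. Largest case (mean −4, SD 2, autocorrelation 0.85): 31.6% to 27.9%, or 3.7 points. With mean −1, SD 1 and no autocorrelation: 59.7% at both visits.
- *Urine, those positive at screening:* fall of 0 to about 14 points. Largest case (mean −4, SD 2, autocorrelation 0.6): 45.8% at baseline, 38.7% at training scan 1, 31.9% at follow-up. The total is 13.9 points, of which 45.8 − 38.7 = 7.1, about half, comes in the lead-in week.
- *TLFB with 28-day look-back:* 28 − 7 = 21 of the baseline days fall before screening. Mean use falls by 0.07 to 0.68 days per 28, and 2.8% to 12.9% of trials show a significant fall.
- *TLFB with 7-day look-back:* the fall is about 0 to 0.12 days per week, and 2.0% to 4.8% of trials are significant.

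**4. Would a pre-feedback trend repair it?** This is a stress test of a remedy, not an estimate of size. Take a stationary two-state process with long-run positivity 40% and a positive urine at screening: P(positive at week k) = 0.40 + 0.60·ρ^|k|. Looking back, the curve rises towards screening just as it falls afterwards. Fit a straight line to weeks −12 to −5 and weeks 1 and 2, then extrapolate to follow-up (k=5).
- Raw fall from k=1 to k=5, for ρ = 0.3, 0.5, 0.7, 0.9: 17.9, 28.1, 31.9, 18.6 points.
- Spurious shortfall against the extrapolated line: 12.5, 23.1, 31.7, 24.8 points.

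Most of the artefact remains, and at ρ = 0.9 it grows. The plain average over weeks −12 to −5 is 40.0%, 40.5%, 44.0% and 65.2%, against follow-up values of 40.1%, 41.9%, 50.1% and 75.4%. A null intervention then shows no spurious fall; the comparison errs towards missing a real one.

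**The case against.** The strongest reply is that the written Aim 1 test is active versus sham, and a concurrent sham arm would largely remove the problem. That would be right if one were enrolled. Under Section I, 1 and the study design in Section I, 4, none is.

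The second reply is that the bias may be negligible. Selection is at screening, not at baseline; the threshold is any use; and if use does not fluctuate in runs and the TLFB windows do not overlap, the fall after baseline is close to nil. This stands, and the lower end of the simulated range shows it. But the TLFB look-back and the screening-to-baseline interval are not stated, so negligible size cannot be shown either.

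Three stronger readings are tempting and are not supported:
- A reader might infer a spontaneous fall of 18 to 32 points from the two-state formula above. That needs everyone to enter on a positive urine exactly one week before baseline and to share one 40% long-run rate. The entry rule is either/or, the interval is not given, and people differ.
- A reader might infer that use is still falling because patients are new to treatment, since Section III, 3 says: "Interested participants entering the methadone treatment program at APT will be referred by APT personnel to research staff when possible for eligibility screening". The requirement of at least 3 months on methadone undercuts this, and the two statements should be read together.
- A reader might call the lead-in week untreated and unused. It is free of feedback, but the baseline transfer run carries the same strategy instructions as the feedback runs. Its urines do enter H1a and the replication correlation in Section I, 13. They are only not used as a comparison.

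**Conclusion.** The point holds for the single-arm design. Some fall in opioid use from baseline can arise without a feedback effect, and no written analysis would distinguish it. The size runs from nil to moderate: about 0 to 4 points in urine positivity overall, up to about 14 among those urine-positive at screening, and up to about 13% false-positive falls if the baseline TLFB overlaps the qualifying month. These figures rest on assumed use rates, assumed fluctuation and a one-week gap from screening to baseline.

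The documents do not support saying that a fall is the expected result of a null intervention. They do support saying that an observed fall would not by itself show a neurofeedback effect. The study can still run; the Aim 1 definitions and conclusion should change.

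**What to change.** 1. Reconcile the one-arm and two-arm text: Section I, 1 and the study design in Section I, 4 against Hypothesis testing, Section I, 13 and the payment text in Section VI, 2.
2. For Aim 1, define baseline as the baseline-scan and training-scan-1 urines and the TLFB days after screening and before the first feedback run, leaving out the window that qualified the participant. Count only later urines and days as outcome. State the TLFB look-back and the screening-to-baseline interval, and specify that the training-scan-1 urine is taken before feedback.
3. Report the change over the feedback-free lead-in week (opioid use, craving, affect) beside the change after first feedback, noting that the baseline transfer run already gives strategy instructions. One week in 24 people will be imprecise.
4. If existing clinic urines are abstracted, compare post-feedback use with the average level before the qualifying window. Do not extrapolate a linear trend.
5. State that Aim 1 gives an uncontrolled pre-post change and does not by itself show a neurofeedback effect.

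Cost: protocol and analysis wording, plus optional abstraction from clinic records that are already consulted for medication compliance. No added visits, scans or patients. The downside is a less favourable and less precise estimate. Steps 2 and 3 expose the drift but do not remove it; only a concurrent control would largely do that.
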